5.4. Handling of Dropouts or Missing Data

5.4.1. Handling of Dropouts or Missing Data for Efficacy Analysis

The daily dose of calcium and vitamin D metabolite/analog will be computed based on both investigator prescribed data and subject diary data. The investigator prescribed data will be considered as the primary method for all efficacy analysis endpoints.

The daily dose of calcium and vitamin D metabolite/analog based on investigator prescription will be determined by using the latest prescribed dose prior to the assessment date of albumin corrected calcium for each analysis visit. To avoid the effect of potential fluctuation of the supplemental medication dose, the prescribed supplemental medication dose at Visit 1 (BL visit) will be excluded from the derivation of the baseline dose and the prescribed dose at the Visit 9 (week 52) for subjects who complete the treatment or Early Termination Visit. Subjects that discontinued early will be excluded from the derivation of the post-baseline prescribed dose.

The average daily dose of calcium and vitamin D metabolite/analog based on subject diaries will be calculated as the average daily dose of a 14-day interval. The 14-day interval for each current analysis visit includes the dose reported during the 14 days on or prior to the assessment date of albumin corrected calcium. However, this 14-day interval should not include or go beyond the assessment date of albumin corrected calcium for the previous analysis visit. If the number of days from the previous albumin corrected calcium date to the current assessment date is less than 14 days, the actual number of days during the two analysis visits will be used to calculate the average daily dose. If the number of days from the previous albumin corrected calcium date to the current assessment date is less than 9 days, the average daily dose will not be calculated and will be classified as missing. Diary data after the last dose date of study drug will be excluded from the derivation.

A missing daily dose of calcium and vitamin D from subject diaries will not be imputed. A minimum 9 days of non-missing data from the intervals is required, otherwise the average daily dose will be classified as missing. Because recordings of dose of calcium and vitamin D metabolite/analog may be missing on different days, different days within the interval may be used in the computation for the daily dose of calcium and for the daily dose of vitamin D metabolite/analog.

For determination of baseline supplemental medication dose, the derivation rules specified in this section will only be applicable when the value of Visit 1 (BL visit) of this study is used as the baseline value. For all other cases, as specified in section 7.3.2, baseline values will be obtained from the REPLACE or RELAY study. The detailed derivation rules are provided in the SAPs for REPLACE and RELAY studies accordingly.

5.4.2. Handling of Dropouts or Missing Data for Safety Analysis

Missing safety parameters will not be imputed.

5.4.3. Handling of Partial Dates

Complete dates will be imputed from partial dates of adverse events and medications solely for the purpose of defining treatment emergence for adverse events and prior/concomitant status for medications. Dates will be defined using the hierarchy of derivations below.

Adverse event or medication start date:

1. If year and month are known, and it is the month and year of the first dose date, use the first dose date.
2. If year and month are known, and it is the month and year of the informed consent, use the informed consent date.
3. If year and month are known, and the month is not the month and year of the first dose or informed consent, use the first day of the month.
4. If only year is known, and it is previous to the year of the informed consent, use June 30th of that year.
5. If only year is known, and it is the year of the informed consent, use the informed consent date.
6. Should any of the previous start dates created be after a complete stop date provided, use the stop date instead of the date that would otherwise be created.
7. Otherwise, if start date is unknown leave as missing.

Medication stop date:

1. If year and month are known and study medication stopped during that month and year, use the stop date of study medication.
2. If year and month are known and informed consent was provided during that month and year, use the date of informed consent.
3. If year and month are known and study medication stopped after the date of informed consent and not in the month that medication stopped, use the last day of the month.
4. If year and month are known and are prior to the month of informed consent, use the first day of the month.
5. If only year is known and study medication stopped during that year, use the stop date of study medication.
6. If only year is known and study medication stopped after that year, use December 31st of that year.
7. If only year is known and study medication stopped prior to that year, use the first day of the year.
8. Should any of the previous stop dates created be before a start date, either a complete date or an imputed one, use the (imputed) start date instead of the date that would otherwise be created.
9. Otherwise, if stop date is unknown leave as missing.

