## 6.4 Description of Study Procedures

### 6.4.1 Visit 1 Baseline Procedures

RELAY study Week 8 procedures must be performed prior to any baseline procedures. Subjects must sign an ICF for this study prior to having any study-related procedures performed. Additionally, REPLACE completers, who did not participate in the RELAY study, will have to undergo ALL Visit 1 procedures.

Subjects will be instructed to come into the study center after having fasted for approximately 6 to 8 hours. Appointments should be scheduled accordingly to accommodate this fasting status (ie, in the morning). The following procedures will be performed prior to enrollment:

- Update the subject's medical history, demographic information, ongoing concomitant medications, and ongoing AEs from the RELAY/REPLACE study
- Review inclusion/exclusion criteria
- Record all new prescription and nonprescription medications, dietary and nutritional supplements, and vitamins and their doses, frequencies, and durations.
- The occurrence of any new or continuing AE, including episodes of hypocalcemia or hypercalcemia, will be recorded following the signing of the ICF, regardless of whether or not study drug had been administered
- Vital signs measurements (prior to blood draws) and weight
- Physical examination
- 12-lead electrocardiogram
- Blood samples for serum chemistries (including calcium, phosphate, and albumin), hematology, serum 25(OH) vitamin D, creatinine clearance, and bone turnover markers. The

blood sample for serum chemistries will be split and a local total serum calcium will also be performed

- Blood sample for PTH and ECP antibodies
- Urinalysis and 24-hour urine calcium, phosphate, sodium, and creatinine
- Serum  $\beta$ -HCG pregnancy test (WOCBP only)
- Urine pregnancy test for immediate confirmation of non-pregnant status (WOCBP only)
- A BMD test by DXA (omit if subject had a scan performed within the past 6 months in either RELAY or REPLACE studies)
- An FSH test to confirm postmenopausal status, EXCEPT if subjects have met the definition of postmenopausal after the beginning the RELAY/REPLACE study (for newly postmenopausal females only)
- The first dose of study medication will be administered after appropriate fasting laboratory evaluations have been taken
- Subjects will be provided with the following study supplies:
  - Study medication cartridges in sufficient number to supply daily doses until the next scheduled clinic visit
  - Two pen injectors

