6.8.1. Adverse Events

Adverse events will be coded using MedDRA Version 13.0. Adverse event listings will provide the verbatim term as well as SOC and PT for each recorded event. A separate listing may be produced to provide the SOC, high level term, PT, and lower level term that are associated with each verbatim term.

Treatment emergent adverse events (TEAEs) are defined as AEs whose onset occurs, severity worsens or intensity increases after receiving the study medication of this study and ≤ 30 days after last dose of study drug. If any AE records contain only partial dates, these will be handled by imputation, as described in Section 7.4.3. AEs which are not treatment emergent will be flagged in listings.

An overview of TEAEs will be summarized using the number and percentage of subjects. The number of events will also be presented except for summaries by highest category. Categories summarized will include any TEAEs, severity of TEAEs (any and highest category), relationship of TEAEs to treatment (any and highest category), treatment emergent serious AEs (TESAEs), severity of TESAEs, relationship of TESAEs to treatment, TEAEs leading to discontinuation, and TEAEs leading to death.

Treatment emergent AEs will be summarized using number and percentage of subjects. Subject incidence for AEs within each SOC and PT will be presented, and the number of events will also be summarized except for summaries by highest category. Categories summarized will be the same as those summarized overall, except that no summary table will be provided for TEAEs leading to death.

Summaries of TEAEs and TESAEs will also be presented by PT. These presentations will be sorted by descending incidence.

Listings will be provided for serious adverse events (SAEs), AEs leading to discontinuation, and AEs leading to deaths.

The incidence of hypocalcemia and hypercalcemia will be identified by clinical preview. Prevalence of hypocalcemia and hypercalcemia will be assessed at all visits on the date of visit. The number of subjects with hypocalcemia and hypercalcemia and the number of episodes of hypocalcemia and hypercalcemia will be assessed for the overall trial.

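### Year-only AE start dates: consent-year onsets go to the consent date and later-year onsets get no date, so on-treatment events can be missed in the TEAE tables

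*SAP*

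**What the plan says.** SAP 5.4.3 completes partial dates "solely for the purpose of defining treatment emergence for adverse events and prior/concomitant status for medications". Four of its seven start-date rules matter here:

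- Rule 1, month and year known: "If year and month are known, and it is the month and year of the first dose date, use the first dose date".
- Rule 4, year only: "If only year is known, and it is previous to the year of the informed consent, use June 30th of that year".
- Rule 5, year only: "If only year is known, and it is the year of the informed consent, use the informed consent date".
- Rule 7, everything left over: "Otherwise, if start date is unknown leave as missing".

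SAP 6.8.1 defines TEAEs as "AEs whose onset occurs, severity worsens or intensity increases after receiving the study medication of this study", up to 30 days after the last dose. For partial dates it refers to Section 7.4.3, which is 5.4.3 in the current numbering. It adds that "AEs which are not treatment emergent will be flagged in listings". It gives no default status for an AE with no onset date.

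On the order of events, Protocol 6.4.1 states: "Subjects must sign an ICF for this study prior to having any study-related procedures performed". It places the first dose after the baseline fasting blood draws.

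**The concern.** Consent can never be later than first dose, so rule 5 pins a year-only onset at or before the start of treatment, however much of that year was spent on drug. Rule 1 settles a smaller uncertainty, within a month, in the opposite direction, towards treatment emergence. For years after the consent year there is no year-only rule, although an onset in such a year will normally fall after treatment began.

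Long-term safety is the primary objective, and the AE summary tables count TEAEs. An event that loses its TEAE status leaves those tables. An event whose status is undefined leaves the choice to whoever programs the tables, possibly after the data have been seen.

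**Working it through.** The plan gives no figure on this point, so there is none to reproduce. The check applies the rules to possible true onsets.

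**Inputs from the documents.** Start-date rules 1, 4, 5 and 7 (SAP 5.4.3); the TEAE window, from first dose to last dose + 30 days (SAP 6.8.1); consent on or before the first-dose date (Protocol 6.4.1); treatment up to 80 months (Protocol 3.2); about 50 subjects (SAP 3.3).

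**Assumptions, not in the documents.** First dose on 20 January, 1 July or 15 December 2011, or 5 January 2012; consent 0, 1 or 14 days before first dose. The worsening route to TEAE status and rule 6 (complete stop date) were left out.

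**Step 1: what the rules do to a true on-treatment onset known only by year.**

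| Year of onset | Rule | Date given | TEAE? |
|---|---|---|---|
| Consent year, consent at least 1 day before first dose | 5 | before first dose | No |
| Consent year, consent on the first-dose day | 5 | first-dose date | Only if day-of-dose onset counts as *after* |
| Any later year | 7, or none | missing | Not stated |

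Reading rule 7 as covering only wholly unknown dates does not help: the later-year onset then has no rule and still gets no date.

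**Step 2: how much of the window each row covers.** By months, the later-year share is (80 − m)/80, with m months left in the consent year: m = 12 gives 68/80 = 85.0%; m = 6 gives 74/80 = 92.5%; m = 1 gives 79/80 = 98.8%. By days, including the 30-day tail, a 1 July 2011 start gives a window of 2,465 days. Of these, 184 fall in 2011 (7.5%) and 2,281 later (92.5%). Over all assumed starts and gaps, the later-year share is:

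- 80 months: 85.3% to 100%
- 72 months: 83.7% to 100%
- 12 months: 8.6% to 100%

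The 100% arises when consent is in December and first dose in January.

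**Step 3: share of possible year-only on-treatment onsets not counted (80 months, 1 July start).**

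| Consent and first dose | Missing onset counted as TEAE | Missing onset not counted |
|---|---|---|
| Same day, day-of-dose onset counts | 0% | 92.5% |
| Same day, day-of-dose onset does not count | 7.5% | 100% |
| Consent at least 1 day earlier | 7.5% | 100% |

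With missing onset counted as a TEAE, the range over all assumed starts is 0% to 14.7% for 80 months.

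**Step 4: effect on a table.** One subject in about 50 is 1/50 = 2 percentage points of incidence. It applies only if that subject has no other qualifying event in the same row.

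**Step 5: check of the replacement dates.** In the first-dose year, the first-dose date is never later than a true on-treatment onset. In a later year, 1 January is after first dose and never later than the true onset. Both dates therefore stay inside the window. With day-of-dose onset counted, 0% of in-window days were misclassified in every scenario run. This covers the replacement dates, not the exceptions listed in the fix.

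**The case against.** Several points against the concern stand.

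- The month-level rules are sound. Rule 1 uses the first-dose date, and rule 3 puts later months inside the treatment period. Only year-only dates are affected, so it would be wrong to say that the partial-date rules as a whole lean away from treatment emergence.
- Consent, baseline procedures and first dose all belong to Visit 1. If they fall on one day, rule 5 gives the first-dose date. Rule 1's use of that date suggests that day-of-dose onset is meant to count, though SAP 6.8.1 does not say so. How often consent came on an earlier day is not stated.
- A reader might infer that every later-year event with a year-only date is lost. The documents do not support that: the status of a missing onset is unspecified, and an AE that worsens on treatment can qualify by that route.
- A reader might also take 85% to 99% as a proportion of AEs. It is a share of follow-up time for a subject treated the full 80 months. The relevant number, AEs with year-only onsets, is not given. It should be small: Protocol 6.2.1.3 asks for start and stop date and time, extension visits are two-monthly, and Protocol 7.1 has all eCRFs source-verified.
- Events leave the summary tables, not the report. Those that are not treatment emergent are flagged in listings, and the listings of SAEs, discontinuations and deaths are not described as limited to TEAEs.

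These points limit the size. They do not give rule 5 a reason to use consent rather than first dose, or supply the absent later-year rule.

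**Conclusion.** The point holds as a gap that should be closed, probably of low frequency. Rule 5 makes a year-only on-treatment onset in the consent year not treatment emergent whenever consent falls on an earlier day than first dose. When the two coincide, the result turns on an undefined *after*. A year-only onset in a later year has no date and no stated TEAE status. For year-only dates, the rules lean towards undercounting.

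The size in events cannot be derived from the documents. For 80 months of treatment, the loss among year-only on-treatment onsets could be anywhere from 0% to 100%, depending on the order of consent and dosing and on how missing onsets are classified. The upper end needs both consent before the dosing day (or a strict reading of *after*) and missing onset treated as not a TEAE; neither is established.

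**What to change.** For AE start dates in SAP 5.4.3, using the original consent date for this study (the term needs defining, because Protocol Table 6-3 has subjects re-consented):

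- (a) Year-only onset in the year of first dose: use the first-dose date, and state that onset on that date counts as treatment emergent.
- (b) Year-only onset in a later year: use 1 January of that year. If the AE was first recorded at a visit after last dose + 30 days (AEs are also collected at the Month 3 and 6 antibody follow-up, Protocol Table 6-4), classify it by that visit.
- (c) Year-only onset in the consent year when first dose is in the next calendar year: keep the consent date.
- (d) Fully missing onset: treat as treatment emergent unless the AE was first recorded after last dose + 30 days.

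In all cases, a complete stop date before first dose makes the AE not treatment emergent. So does a record as ongoing from RELAY or REPLACE without worsening. The second exception matters because Protocol 6.2.1 carries ongoing AEs into this study; without it, (a) and (d) would turn some of them into TEAEs.

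The cost is a few lines of SAP text and code. A few pre-dose events may be counted as TEAEs, which is the conservative direction for a safety study.

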5.5. Interim Analyses and Data Monitoring

Two interim study reports will be completed: 3-year interim analyses to look at safety and efficacy compiled through 31 May, 2013; 5-year interim analyses to look at safety and efficacy compiled through 08 May 2017. There is no DSMB identified for this study.

5.6. Multicenter Studies

Center will not be used as a covariate factor in the analysis.

5.7. Multiple Comparisons/Multiplicity

Not applicable.

5.8. Active-Control Studies Intended to Show Non-inferiority or Equivalence

There is no active control in the current study

5.9. Examination of Subgroups

Subgroup analysis by gender will be performed for the primary efficacy endpoint. Additional subgroup analysis may be explored as appropriate. Subgroup results need to be interpreted with caution if there is insufficient number of subjects in a subgroup.

6. Statistical Analysis

6.1. Disposition of Subjects

Subject disposition will be summarized for all subjects enrolled as well as subjects in each analysis population.

The number and percentage of subjects assessed at each planned visit, subjects completing the treatment (based on the study exit CRF at Visit 9 (week 52), completing the study (based on the study exit CRF and finish the follow-up Visit 11 (week 56), and discontinuation by reasons will be summarized

6.2. Protocol Deviations

Protocol deviations will be identified programmatically as well as based on protocol deviations collected by the study monitors. A summary table and listing of all collected protocol deviations might be presented upon request.

6.3. Analysis Populations

The analysis populations to be used in this study are the Safety Population and the Intent-to-Treat (ITT) Population.

The Safety Population includes all subjects who received at least one dose of study drug with any follow-up information. All safety analyses will be conducted on this population.

The ITT population includes all subjects who received at least one dose of study drug and had at least one efficacy measurement. The primary and secondary efficacy analyses will be based on the ITT population.

6.4. Demographic and Other Baseline Characteristics

Demographic variables (such as sex, age, race, etc.) and medical history will be obtained; medical history will be reviewed and updated as necessary from the RELAY or REPLACE study, if available, for subjects previously enrolled in those studies.

Descriptive statistics will be used to summarize the baseline and demographic characteristics. Demographic and baseline characteristics to be presented include:

- age (in years, both as a continuous parameter and by categories of <45, 45-64, >=65)
- gender
- race
- ethnicity
- height (cm) at the baseline visit
- weight (kg) at the baseline visit
- body mass index (BMI) (kg/m²) at the baseline visit

Medical and surgical history will be coded using the Medical Dictionary for Regulatory Activities (MedDRA)², Version 13.0. The history will be summarized by system organ class (SOC) and preferred term (PT) within system organ class for the Safety Population, with both SOC and PT sorted alphabetically.

6.5. Measurements of Treatment Compliance

The data for study medication use are reported in the paper diary. Percent treatment compliance will be calculated as:

[100*doses administered / days on treatment], where days on treatment is calculated as (date of last dose - date of first dose) + 1.

Subjects will be considered compliant overall for study medication if the calculated compliance is $\geq 80\%$ to $\leq 120\%$. Overall treatment compliance will be presented using descriptive statistics and the number and percentage of subjects who are $\geq 80\%$ to $\leq 120\%$ compliant will be presented for the Safety Population.

6.6. Extent of Exposure

6.6.1. Exposure during this (RACE) study

The extent of exposure is defined as the number of days on treatment, calculated as:
(date of last dose - date of first dose) + 1.

The date of the first dose is based on CRF entry. The date of the last dose will be based on information collected in the paper diary. The extent of exposure and the number of days that the dose was administered will be summarized. The extent of exposure will also be categorized into weeks (<1, 1-<4, 4-<8, 8-<16, 16-<24, 24-<32, 32-<40, 40-<48, 48-<52, ≥ 52) and tabulated. Exposure summaries will be presented for the Safety Population. Number of subjects at different dose level at EOT will be summarized as specified in section 8.7.2.

6.7. Analysis of Efficacy

All efficacy analyses will be conducted on the ITT Population.

Prescriptive analyses will be presented by visit in order to see how the status or value changes over time. The EOT status or value will be included as a separate time point in the summary.

Efficacy endpoints based on the calcium and/or calcitriol supplement will be derived using both the investigator prescribed data and subject diary data. Computation of daily calcium and calcitriol dose is specified in Section 7.4.1. Analysis based on the investigator prescribed data will be primary. Analysis based on the subject diary data will be considered as supportive.

6.7.1. Primary Analysis

As specified in the definition of efficacy endpoint, the subject must meet three conditions at Week 52 and/or EOT to be considered a responder. First, the subject's prescribed daily oral calcium supplementation should be reduced by at least 50% from baseline or an oral calcium dose of ≤ 500 mg; second, the subject's prescribed daily oral calcitriol supplementation dose should be reduced by at least 50% from baseline or an oral calcitriol dose of ≤ 0.25 μg . For the third condition, albumin-corrected total serum calcium concentration should be normalized or maintained compared to the baseline value (≥ 7.5 mg/dL) and does not exceed the ULN for the central laboratory. Different maintenance ranges for this third condition will be assessed in the sensitivity analysis (Section 8.7.5).

The calculation of daily calcium and calcitriol dose is specified in Section 7.4.1. The determination of responders using the subject diary dose data instead of prescribed dose will be used as one of the supportive analyses to the primary analysis.

The number and percentage of responder status will be presented. No formal statistical test will be done. A bar chart for percent of subjects who achieve responder status will be plotted. The percent of subjects who achieve calcium supplement response criterion, and the percent of subjects who achieve calcitriol supplement response criterion will also be plotted in a bar chart.

No statistical testing will be conducted to compare between group differences.

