Wording was clarified for the schedule of follow up visits and procedures for subjects with PTH-specific antibodies at the final 2 visits (rather than the final visit).	Low levels of detectable antibody tend to be variable and of no known clinical significance.	Table 6-3, Table 6-4
Wording was added to clarify that additional interim analyses may be performed as necessary to support regulatory interactions and/or publications.	Updated information.	Section 8.6.3
Removed ( $\geq 7.5$ mg/dL) from the baseline value of albumin-corrected total serum calcium concentration since this was an inadvertent carryover from the previous study, REPLACE. Sentence now reads: An albumin-corrected total serum calcium concentration that is normalized or maintained compared to the baseline value ( <del><math>\geq 7.5</math> mg/dL</del> ) and does not exceed the ULN for the central laboratory	Correction.	Synopsis, Section 2.3.2, Section 8.3

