### **8.6.2 Handling of Dropouts or Missing Data**

No safety data will be imputed. The missing patterns of the efficacy variables will be assessed and an unbiased imputations method will be documented in the SAP.

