SI	International System of Units
SOC	System Organ Class
TEAE	Treatment Emergent Adverse Event
TESAE	Treatment Emergent Serious Adverse Event
ULN	Upper Limit of Normal
WBC	White Blood Cell
WHO	World Health Organization

1. Introduction

This document describes the rules and conventions for data handling and methodologies for statistical analysis to be used in the presentation and analysis of efficacy and safety data for protocol PAR-C10-008 (RACE). It describes, in detail, the data and variables to be summarized and analyzed, including specifics of the statistical analyses to be performed. This statistical analysis plan is based on Protocol Amendment 6, dated October 24, 2016.

Hypoparathyroidism is a condition in which there is deficient production of parathyroid hormone (PTH) from the parathyroid glands. The deficiency of PTH results in decreased calcium reabsorption from renal tubules, malabsorption of calcium from the gastrointestinal (GI) tract and reduced calcium mobilization from bone. Hypoparathyroidism is the most common cause of chronic hypocalcemia.

NPSP558 (rhPTH[1-84]) is recombinant human parathyroid hormone that is identical in structure to endogenous human parathyroid hormone (hPTH), a single-chain polypeptide consisting of 84 amino acid residues (rhPTH[1-84]). This is a 12-month open-label study investigating the safety and tolerability of NPSP558 for the Treatment of Adults with Hypoparathyroidism.

A Phase 3 study is currently ongoing (CL1-11-040, REPLACE) to investigate the effects of daily subcutaneous (SC) injections of rhPTH[1-84] at doses of 50, 75, or 100 µg. An 8-week study of fixed doses of 25 and 50 µg (PAR-C10-007, RELAY) is currently being undertaken to explore a broader range of treatment dose options.

2. Study Objectives

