4.2. Efficacy Endpoint

The proportion of subjects in whom the following three conditions are fulfilled at Week 52 (Visit 9) and/or at the End of Treatment will be summarized:

- $A \geq 50\%$ reduction from baseline in dose of oral calcium supplementation or an oral calcium dose of ≤ 500 mg **AND**
- $A \geq 50\%$ reduction from baseline in dose of oral calcitriol supplementation or an oral calcitriol dose of ≤ 0.25 μg **AND**
- An albumin-corrected total serum calcium concentration that is normalized or maintained compared to the baseline value and does not exceed the ULN for the central laboratory

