6.7.5. Sensitivity Analyses

There is no sensitivity analysis planned for this study.

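### SAP 6.7.1 puts a 7.5 mg/dL value in the responder rule that the protocol and SAP 4.2 do not have, and its wording on time point and early discontinuers is ambiguous

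*SAP*

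**What the plan says.** **Protocol (Amendment 6).** The Synopsis and Sections 2.3.2 and 8.3 define one composite of three conditions: calcium dose, calcitriol dose and albumin-corrected serum calcium. The proportion meeting all three is to be summarized at Week 52 and at End of Treatment. The calcium condition contains no 7.5 mg/dL value.

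**SAP 4.2.** The calcium condition matches the protocol: "An albumin-corrected total serum calcium concentration that is normalized or maintained compared to the baseline value and does not exceed the ULN". The time point is given as Week 52 and/or End of Treatment.

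**SAP 6.7.1.** The calcium condition becomes "albumin-corrected total serum calcium concentration should be normalized or maintained compared to the baseline value (≥ 7.5 mg/dL) and does not exceed the ULN", and "the subject must meet three conditions at Week 52 and/or EOT to be considered a responder". Other maintenance ranges are deferred to a sensitivity analysis in a Section 8.7.5.

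**SAP 6.7.5.** "There is no sensitivity analysis planned for this study".

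**SAP 1 and 3.4.2.** "This statistical analysis plan is based on Protocol Amendment 6, dated October 24, 2016", and no departures from the protocol's analyses are declared.

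**SAP 5.4.1.** "Subjects that discontinued early will be excluded from the derivation of the post-baseline prescribed dose". Protocol 8.6.2 had said that "an unbiased imputations method will be documented in the SAP".

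**The concern.** The SAP holds two versions of the same endpoint. Only the one in 4.2 agrees with the protocol on the calcium condition, and 6.7.1 is the section that spells out how a subject is classified. Two programmers working from the two sections could produce different tables, each able to cite the SAP.

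This is the study's only composite efficacy endpoint. It also feeds the by-visit responder table, the carbonate versus citrate comparison (which serves a secondary objective) and the subgroup analysis by gender.

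The study is open-label. The SAP is dated March 2018 and lists interim efficacy reports on data through May 2013 and May 2017. An unsettled rule is therefore best closed by reference to the protocol, not by a choice made at programming.

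**Working it through.** There is no planned figure to reproduce. The sample size of about 50 is a rollover estimate, and no testing is planned. The check is a comparison of texts, with arithmetic only to show what the ambiguities could do.

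**1. The 7.5 mg/dL value.** It is absent from all three protocol statements of the endpoint and from SAP 4.2, and present in SAP 6.7.1. As background, the protocol's summary of changes says of the same value that "this was an inadvertent carryover from the previous study, REPLACE". The SAP's modification history mentions only the design description and the schedule tables as updated for Amendment 6. The likeliest explanation is that 6.7.1 was missed.

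**2. Direction of effect.** Take *maintained* to mean at or above baseline (the documents do not define it). Take the normal range as 8.4 to 10.2 mg/dL, the general range in Protocol 1.1, because the central laboratory range is not given. Two invented subjects:

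| Reading of the bracket | Baseline 7.2, value 7.3 | Baseline 8.6, value 7.8 |
|---|---|---|
| Protocol and SAP 4.2 (no bracket) | meets | fails |
| Extra floor on the response value | fails | fails |
| 7.5 replaces the baseline comparison | fails | meets |
| Describes baseline | undefined, baseline is below 7.5 | fails |

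An extra floor can only lower the rate. A replacement can raise it. A description of baseline changes nothing except for subjects who start below 7.5. The size depends on the joint distribution of baseline and on-treatment calcium, which the documents do not give.

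**3. The sensitivity analysis.** The SAP has no Section 8.7.5. Its internal references run two section numbers high (7.4.1 for 5.4.1, 7.9 for 5.9, 8.7.2 for 6.7.2), so the intended target is almost certainly 6.7.5, which plans none.

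**4. Week 52 and/or EOT.** The wording permits three tables: two separate proportions, response at either time, or response at both. With response probability p at each time and within-subject correlation ρ (both assumed):

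- P(both) = p² + ρp(1−p)
- P(either) = 2p − P(both)
- difference = 2p(1−p)(1−ρ)

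At p = 0.60:

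| ρ | Both | Single time point | Either |
|---|---|---|---|
| 0 | 36% | 60% | 84% |
| 0.5 | 48% | 60% | 72% |
| 0.8 | 55% | 60% | 65% |
| 1 | 60% | 60% | 60% |

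Over p = 0.5 to 0.7 and ρ = 0 to 0.8 the gap between either and both runs from about 8 to 50 points.

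**5. Early discontinuers.** The sentence in 5.4.1 before the quoted one stops at the Early Termination Visit without finishing its clause. Joined, the two most naturally say that the prescription written at Visit 9 (completers) or at early termination (discontinuers) is not used. Read alone, the second sentence leaves discontinuers with no prescribed dose after baseline, hence no status in the prescribed-dose analysis, which SAP 6.7 makes primary. That conflicts with SAP 6.3, which keeps them in the ITT population, and with SAP 5.1, which defines EOT as the last on-treatment measurement.

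Illustration, all rates assumed: of 50 subjects, 10 stop early and respond at 30%, and 40 continue and respond at 70%.

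- Discontinuers excluded: 28/40 = 70%
- Discontinuers kept with their own status: (28 + 3)/50 = 62%
- Discontinuers counted as non-responders: 28/50 = 56%

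**The case against.** The strongest reply is that the time point and the discontinuers are largely handled elsewhere. SAP 5.1 and 6.7 treat EOT as its own time point, and 6.7.2 tabulates the endpoint by visit, so both proportions the protocol asks for should appear. The ITT and EOT definitions keep early discontinuers. The primary objective is safety and nothing is tested. Most of this stands. It is why these two items are ambiguities to repair and not settled departures from the protocol.

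Three stronger readings are tempting, and the documents do not support them.

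- **That 7.5 mg/dL inflates response, because values of 7.5 to 7.9 would pass while Appendix 2 treats calcium below 8.0 as low.** This needs the bracket to replace the baseline comparison, which the text does not say. Appendix 2 also substitutes the subject's own baseline for those who entered below 8.0. With an assumed mean of 8.5 to 8.7 and SD of 0.5 to 0.7, about 7.3% to 16.1% of values lie between 7.5 and 8.0. That is not the share reclassified, since 8.0 is not part of the responder rule.
- **That the SAP adopts an either-time rule.** Its separate EOT summary points the other way.
- **That the SAP drops early discontinuers.** This takes a broken sentence literally against two definitions.

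The reply does not touch the 7.5 mg/dL mismatch or the reference to an unplanned sensitivity analysis.

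**Conclusion.** The point stands in this form. The 7.5 mg/dL value in SAP 6.7.1 contradicts the current protocol, SAP 4.2 and the SAP's own statement that nothing departs from the protocol. The sensitivity analysis that 6.7.1 relies on is not planned. Both follow from the text alone.

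The direction and size of the effect on the responder proportion are not established. The time-point and early-discontinuer wordings are ambiguous. The figures above show how far apart the readings could lie under assumed rates, correlations and discontinuation, and they do not predict this trial's result. Separately, the SAP does not say how an ITT subject without a derivable responder status is counted, although the protocol promised a method. What is at stake is the reported proportion and the by-visit, calcium-source and gender summaries built on it.

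**What to change.** - **SAP 6.7.1:** delete the 7.5 mg/dL bracket so that the rule matches SAP 4.2 and the protocol. If it is meant, declare and explain it in SAP 3.4.2 and say which value it applies to.
- **SAP 4.2 and 6.7.1:** replace the and/or wording with two separately reported proportions, one at Week 52 and one at EOT. Both sections need the change.
- **SAP 6.7.5:** either specify the maintenance-range sensitivity analysis or delete the reference to it in 6.7.1.
- **SAP 5.4.1:** rewrite the broken sentence so that only the prescription written at Visit 9 or the Early Termination Visit is excluded, not the subject.
- **Denominator:** state it for each proportion, and state how ITT subjects without a derivable status are handled. Show non-responder counting as a sensitivity analysis. It is not an unbiased method in itself: in the illustration it gives 56% where keeping each subject's own status gives 62%.

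The cost is minor rewording and reprogramming, with no new data. The reported rate may change.
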